3.6. Adverse Events

3.6.1. Method of Determining Adverse Events

Safety assessments will include recording AEs reported spontaneously by the subject or collected by the Investigator. AEs will be recorded at each visit throughout the study on the appropriate CRF. Every attempt should be made to describe the AE in terms of a diagnosis. If a clear diagnosis has been made, individual signs and symptoms will not be recorded unless they represent atypical or extreme manifestations of the diagnosis, in which case they should be reported as separate events.

Subjects should be asked whether, since the time of the last observation or visit, they had any of the following:

- Experience any changes in well-being;
- Used any new medications;
- Changed medication regimens (both prescription and OTC); and/or
- Were admitted to a hospital or had any accidents.

All questions should be of a general nature and should not suggest symptoms.

When an AE is suspected, all relevant evaluations will be carried out and appropriate treatment provided. Additional follow-up will be done as necessary ([Section 3.6.4](#)) and recorded in the subject's source documents, and the results will be provided to the Sponsor.

For AE definitions and reporting requirements refer to [Section 3.6.2](#) and [Section 3.6.3](#).

Note: Any observed response which can be denoted using the irritation criteria summarized in [Table 3](#) and [Table 4](#) will not be considered an AE. Likewise, any tape-related irritation will only be noted as an AE when all patches are discontinued due to tape reaction around all sites (see [Section 3.6.6](#)).

3.6.2. Adverse Event Definitions

3.6.2.1. Adverse Events

Information about all local and systemic AEs, whether volunteered by the subject, discovered by Investigator questioning, or detected through other means, will be collected and recorded on the AE CRF and followed as appropriate.

An AE is defined as any untoward medical occurrence in a patient or clinical investigation subject administered a pharmaceutical product (or cosmetic product), which does not necessarily have a causal relationship with this treatment. An AE can therefore, be any unfavorable and

unintended sign, symptom, or disease temporally associated with the use of a medicinal investigational product, whether or not considered related to the medicinal investigational product.

Adverse Events will be coded using an internationally recognized dictionary (MedDRA).

Medical conditions/diseases present before starting study treatment are considered AEs only if they worsen after starting study treatment (any procedures specified in the protocol). Any AEs occurring before starting study treatment but after signing the ICF are recorded on the Medical History/Current Medical Conditions CRF.

To the extent possible, each AE will also be described by:

1. its duration (start and end dates),
2. the severity grade (mild, moderate, severe)
3. its relationship to the study drug,
4. the action(s) taken, and
5. as relevant, the outcome.

Note: Any observed response which can be denoted using the irritation criteria summarized in [Table 3](#) and [Table 4](#) will not be considered an AE. Likewise, any tape-related irritation will not be noted as an AE.

3.6.2.2. Serious Adverse Events

A “SAE” is any AE that:

- Results in death;
- Is life-threatening (Note: the term “life-threatening” refers to any AE that, as it occurs, puts the subject at immediate risk of death. It does not refer to an AE that hypothetically might have caused death if it were more severe).
- Results in hospitalization or prolongation of current hospitalization (not including hospitalization for a pre-existing condition that has not increased in severity or frequency from the subject’s underlying medical condition prior to entry into the study).
- Is a congenital anomaly/birth defect in the offspring of a subject.
- Is another serious (important medical events) event.
- Results in persistent or significant disability/incapacity.

(Note: Important medical events may not be immediately life-threatening or result in death or hospitalization but may be considered serious when, based on the appropriate medical judgment, they may jeopardize the subject or require medical or surgical intervention to prevent one of the outcomes listed above. Examples of such medical events include allergic bronchospasm requiring intensive treatment in an emergency room or at home; blood dyscrasias or convulsions that do not result in inpatient hospitalization; or development of drug dependency or drug abuse.)

3.6.2.3. Severity of Adverse Events

“Severity” of the AE refers to the extent to which an AE affects the subject’s daily activities and differs from “Serious,” which is a regulatory classification.

The Investigator is to classify the severity of an AE according to the following definitions:

- **Mild:** The symptom has a negligible effect or no impairing effect on the subject’s normal function.
- **Moderate:** The symptom impairs the subject’s normal function to some extent.
- **Severe:** The symptom has an obvious, significantly impairing effect on the subject’s normal function.

3.6.2.4. Relationship of Adverse Events to Study Treatments

The Investigator is to classify the drug relationship of an AE according to the definitions outlined in [Table 5](#).

Table 5: Relationship of AE to Study Drug

Association	Definition
Not related	(1) the existence of a clear alternative explanation (e.g., mechanical bleeding at surgical site) or (2) non-plausibility, e.g., the subject is struck by an automobile or cancer developing a few days after drug administration.
Unlikely	There is no medical evidence to suggest that the AE may be related to study drug usage, or there is another more probable medical explanation.
Possible	There is medical evidence to suggest that there is a reasonable possibility that the AE may be related to study drug usage. However, other medical explanations cannot be excluded as a possible cause.
Probable	There is strong medical evidence to suggest that the AE is related to study drug usage.
Definite	A clinical event, including laboratory test abnormality (if applicable), in which there is no uncertainty in its relationship to test drug (e.g., positive Rechallenge).

3.6.3. Reporting Adverse Events

Adverse events that occur from the time of informed consent through completion of the last study visit should be reported.

Every attempt should be made to describe the AE in terms of a diagnosis. If a clear diagnosis has been made, individual signs and symptoms will not be recorded unless they represent atypical or extreme manifestations of the diagnosis, in which case they should be reported as separate events. If a clear diagnosis cannot be established, each sign and symptom must be recorded individually.

Any SAEs occurring in a subject receiving study drug must be reported to the Sponsor within 24 hours of the site being informed of the event, even if the event does not appear to be drug-

related. The report must be made by sending a completed SAE Report form to the Sponsor. Any pertinent follow-up information should be provided in a similar manner. Contact information is provided in [Section 3.7.1](#).

3.6.4. Adverse Event Follow-up

Any ongoing AE at the time of study completion or withdrawal will be followed until the AE is resolved or the subject is referred to his/her own PMD. The Investigator and the Sponsor will decide if longer follow-up is appropriate on a case-by-case basis. Subjects who experience any clinically significant AE will remain under medical supervision until the Investigator or the Sponsor's Medical Monitor deems the AE to be resolved, stabilized, or no longer serious enough to warrant follow-up.

3.6.5. Pregnancy reporting

Prior to study enrollment, females of childbearing potential must be advised of the importance of avoiding pregnancy during study participation and the potential risk factors for an unintentional pregnancy. The signed Informed Consent Form must document this discussion.

A UPT will be performed on all females of childbearing potential at Day 1 (day of first patch application) and EOS. All women of childbearing potential will receive a UPT prior to the first study drug administration and the study drug must be withheld until the results of laboratory pregnancy testing are available. If pregnancy is confirmed, the subject must not receive any study drug and must not be enrolled in the study.

3.6.6. Expected Adverse Events

Any observed response in the patch test area that can be denoted using the irritation criteria summarized in [Table 3](#) and [Table 4](#) will not be considered an AE.

Tape related reactions will only be recorded as AEs when the subject is discontinued due to tape reaction around all sites. When 1 or 2 sites are experiencing severe tape related reactions, the application site will be stopped and the subject will continue on the study.

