If at the time of refusal a study product has already been administered, the subject should be advised on follow-up safety investigations. If a subject withdraws from the study, all efforts will be made to complete a final evaluation if possible. Subjects discontinued for having experienced an AE will be followed until the AE is resolved, a reasonable explanation is provided for the event, or the subject is referred to his/her own primary medical doctor (PMD). The specific AE in question will be recorded on the appropriate CRF.

If a subject develops a serious adverse event (SAE), his/her termination from the study will be considered by the Investigator. Similarly, if the subject develops conditions over the course of

the study which would have excluded his/her entry in the study according to the safety-related medical exclusion criteria, he/she must be withdrawn immediately.

The subject may be withdrawn from the study at any time at the discretion of the Investigator for medical reasons and/or due to non-adherence to the treatment scheme and other duties stipulated in the study protocol. The reasons are to be documented on the CRF.

In addition, the Sponsor retains the right to end the study at any time if the study cannot be carried out as agreed upon in the protocol. In case of premature termination or suspension of the study, the Sponsor's study manager will promptly inform the Investigator/institutions and regulatory authorities of the termination or suspension and the reason for that. It is the responsibility of the Principal Investigator (PI) to notify the Institutional Review Board (IRB) in the case of premature termination/suspension.

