3.5.7. Safety Assessments

3.5.7.1. Patch Test Site Evaluations

For both Induction and Challenge Phases, after 24 hours (± 2 hour) of product application, all sites will be evaluated and one application site of each product and the additional untreated site will be irradiated. The sites will be examined for dermal reactions at approximately 24 hours (± 4 hours), 48 hours (± 4 hours), and 72 hours (± 4 hours) post-irradiation.

The scores in [Table 3](#) will be used to express the response observed at the time of examination and will be recorded on the subjects' CRFs. The score will be used for statistical analysis. Additional response notations are presented in [Table 4](#).

Table 3: Response Scores

Response	Symbol	Numerical Equivalent Score
Erythema		
No reaction	-	0
Mild, but definite erythema	+	1
Moderate erythema	++	2
Marked/severe erythema	+++	3
Edema		
No reaction	-	0
Mild, but definite edema	**	1
Definite edema with erosion/vesiculation	***	2

Table 4: Notations

Response/Comment	Notation
Hyperpigmentation	Hr
Hypopigmentation	Ho
Vesiculation	V
Papular response	p
Papulovesicular response	pv
Damage to epidermis: oozing, crusting, and/or superficial erosions	D
Itching	I
Spreading of reaction beyond patch study site (ie, reaction where material did not contact skin)	S
Follicular irritation with or without pustule formation (folliculitis)	f
Subject absent	X
Patch dislodged	PD
Not patched	NP
No reaction	0

The readings will be made under a standardized white light source.

The 3-week period of patch contact during the Induction Phase may result in tape-related irritation in some individuals. Tape related irritation will not be graded as an irritant response at the patch site but will be noted separately on the CRF.

The Investigator will assess the reactions seen during the Challenge Phase and determine whether the subject is photosensitized or not. The following guidelines are generally considered in this assessment. Not all observations of erythema and edema are associated with photosensitivity; only if erythema and edema are observed can a reaction be suspected of being a positive photosensitivity reaction. An increase in the intensity of the reaction over time further

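### Every patch-site response that can be scored is excluded from adverse events without exception, so as written a serious or discontinuing product reaction is not covered by SAE reporting or required follow-up

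*Combined protocol and SAP*

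**What the plan says.** The exclusion appears three times. Section 3.6.6 applies it to "Any observed response in the patch test area that can be denoted using the irritation criteria summarized in" Tables 3 and 4. Section 3.6.1 words it as "Any observed response which can be denoted using the irritation criteria summarized in" the same tables and says that such a response "will not be considered an AE". Section 3.6.2.1 repeats the Section 3.6.1 wording inside the AE definition. Only Section 3.6.6 limits the rule to the patch test area.

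The two tables (Section 3.5.7.1) run to the severe end. Erythema goes up to marked/severe (score 3), and the top edema score of 2 is "Definite edema with erosion/vesiculation". Notation D is "Damage to epidermis: oozing, crusting, and/or superficial erosions", and notation S is "Spreading of reaction beyond patch study site (ie, reaction where material did not contact skin".

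Other sections depend on AE status or assume it:

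- Section 3.3.3, repeated in Section 3.3.4: "Subjects discontinued for having experienced an AE will be followed until the AE is resolved", explained, or handed to the subject's own doctor.
- Section 3.6.2.2 defines an SAE as an AE that meets a listed criterion.
- Table 5 (Section 3.6.2.4) describes a definite relationship as one with "no uncertainty in its relationship to test drug (e.g., positive Rechallenge").

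**The concern.** Keeping routine scored irritation out of the AE listing is sensible, because the scores are an endpoint in their own right. The difficulty is that the rule has no upper limit. It treats mild erythema and an eroded reaction that ends participation in the same way: both can be scored, so neither is an AE.

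AEs are one of the three safety endpoints named in the Synopsis and Section 3.1. AE status also triggers the protocol's safety duties. If the rule is followed exactly, a product-site reaction that is serious or forces a subject out brings no SAE report and no required follow-up to resolution. Where the subject leaves during Induction, the reaction may also be missing from the planned reaction analyses.

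**Working it through.** The plan has no figure to reproduce here, so the check traces a reaction through the rules.

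**Step 1. Can the reactions of concern be scored?**

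| Reaction | Where it sits (Section 3.5.7.1) | AE under the rule? |
|---|---|---|
| Severe erythema | Table 3, erythema 3 | No |
| Erosive or vesicular | Table 3, edema 2; Table 4, V or D | No |
| Spreading beyond the patch | Table 4, S | No under 3.6.1 and 3.6.2.1; arguable under 3.6.6 |
| Skin signs of photosensitivity | Erythema plus edema, both in Table 3 and both required before a positive is suspected | No |

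**Step 2. What depends on AE status?**

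- SAE classification (3.6.2.2), and with it 24-hour reporting (3.6.3, 3.7.2, 3.7.3).
- Follow-up after discontinuation (3.3.3, 3.3.4) and of events ongoing at study end or withdrawal (3.6.4).
- The duty to report an unusual frequency of AEs within 24 hours (3.7.2). A run of erosive reactions would not count towards it.

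**Step 3. Which other analyses capture the reaction?** Section 4.6.1 tabulates all Induction and Challenge scores. Section 4.6.2 tabulates photosensitization, with a 95% confidence interval if any occurs. Section 4.3 restricts who is counted: local tolerability uses Induction completers and photosensitization uses Challenge completers. Both definitions require at least 6 applications/irradiations and at least 11 Induction evaluations. The regular schedule in Section 3.1 supplies exactly those numbers:

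- applications: 2 per week × 3 weeks = 6, hence 6 patch-removal readings;
- post-irradiation readings: 6 − 1 = 5, because none follows the last Friday;
- total: 6 + 5 = 11.

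(Section 3.5.1 opens by calling Induction a series of 4 applications. That must be reconciled with Sections 3.1 and 4.3; the count above uses 6.)

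A subject stopped before the sixth application therefore cannot be a completer. Section 3.3.3 foresees such cases: erythema 2 with edema 1 after the first sequences may lead to discontinuation. That subject is in neither reaction population. The one population that keeps the subject is all treated subjects, evaluable for AEs, and there the reaction is excluded by definition.

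**Step 4. Do the sections agree with each other?**

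- Table 5 uses a positive Rechallenge as its example of a definitely related AE. Rechallenge responses are graded as dermal reactions (3.5.1), so under the rule they are not AEs.
- Tape reactions around all sites become AEs when patching or participation stops because of them (3.6.1, 3.6.6). Product reactions have no such provision, and Section 3.6.2.1 says tape irritation is not noted as an AE at all.

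**Step 5. How likely is the gap to matter?** The documents give no rate p for reactions that are serious, discontinuing or diagnosed as sensitization. Assuming independent subjects and n = 50, the chance of at least one is 1 − (1 − p)^50:

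| Assumed p | Chance of at least one |
|---|---|
| 1% | 39.5% |
| 2% | 63.6% |
| 5% | 92.3% |

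The 50 are evaluable subjects. At least that many will be treated, so for a given p these are minimum chances.

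**The case against.** The strongest reply is that the protocol sends local reactions to their own endpoints by design. Irritation responses and positive Challenge responses are named alongside AEs, and keeping them apart avoids double counting. For subjects who complete, this stands: the question is which table shows the reaction, not whether it is reported.

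The rule can also be read more narrowly. It excludes an observed response, whereas photosensitization is an Investigator's diagnosis, and Sections 3.6.1 and 3.6.3 ask for AEs to be described as diagnoses. Table 5 may then be consistent, or may simply be generic causality text. This makes diagnosed photosensitization an ambiguity rather than a clear exclusion. It does not help a severe or discontinuing reaction that carries no such diagnosis.

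There are partial safeguards. A final evaluation is attempted on withdrawal (3.3.3, 3.3.4). Subjects who refuse further participation after dosing are advised on follow-up investigations (3.3.3). Rechallenge waits until Challenge reactions have resolved (3.5.1). None requires follow-up to resolution for a reactor who leaves.

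It could also be argued that Section 4.6.1 names no population, so its score counts might include early leavers. But Section 4.3 assigns local tolerability to Induction completers, and nothing overrides it.

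A reader might infer that the AE tables would be empty, or that local AE incidence is zero by construction. The documents do not support that. Local events that Tables 3 and 4 cannot denote remain AEs, as do unrelated events. Systemic features or a hospitalization could still be reported as an AE or SAE. Nor would a confirmed photoallergic subject who completes Challenge be invisible, because Section 4.6.2 counts that subject.

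**Conclusion.** The concern holds as a gap in recording and reporting rules. Three sections exclude every scorable response from AEs, with no exception for seriousness, discontinuation or diagnosed sensitization. SAE status, required follow-up and 24-hour reporting consequently do not reach such a product-site reaction as written. The gap is clearest for a subject discontinued during Induction, who has no AE for the reaction and is in neither reaction population. It is narrowest for a Challenge completer, whose reaction is reported through Sections 4.6.1 and 4.6.2.

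Confirmed photosensitization is not the best example of a reaction that ends participation, since it is established at Challenge or Rechallenge, the last procedures. Reactions during Induction are.

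The conclusion rests on following the text literally and on Section 4.3 governing the score summaries. How many subjects would be affected cannot be derived from the documents; the chances under Step 5 depend wholly on assumed rates. The sponsor should make this change: it closes a reporting gap and removes two internal conflicts, but does not alter the photosensitization analysis in completers.

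**What to change.** Add one exception, worded identically, to Sections 3.6.1, 3.6.2.1 and 3.6.6. A scored patch-site response is additionally recorded as an AE when it (a) meets a seriousness criterion in Section 3.6.2.2, (b) leads to discontinuation of the subject, or (c) is diagnosed by the Investigator as photosensitization or contact sensitization. Any further clinical threshold, such as spread or need for treatment, is for the sponsor and the investigator to decide.

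In the same edit, reconcile the tape-reaction statements in the three sections, and confirm that the Table 5 example is consistent with the exception. Because all treated subjects are evaluable for AEs, the exception also brings subjects stopped during Induction back into a planned table and under the existing follow-up rules.

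The cost is protocol wording and a few more AE forms. Scoring, score analyses and the photosensitization summary stay as they are. A few reactions will appear in both the score and AE tables, which a footnote can explain.

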3.7.2. Reporting Responsibility

Any death, SAE, pregnancy, (see [Section 3.6](#)), or unusual frequency of AEs, must be reported immediately (i.e., not later than 24 hours after first learning of its occurrence) to the Sponsor's study manager by the Investigator, even if the event(s) appear to be unrelated to study treatment. Follow-up information about a previously reported SAE or pregnancy must also be reported to the Sponsor within 24 hours of receiving it. If the SAE or pregnancy has not been previously documented (i.e., is a new occurrence) and it is thought to be related to the investigational product (or therapy), the Sponsor may contact the Investigator to obtain further information. If warranted, an investigator alert may be issued, to inform all Investigators involved in any study with the same product (or therapy) that this SAE or pregnancy has been reported.

The IRB should also be notified of SAEs or pregnancies and of any follow-up information in writing, as is practical, and depending on local regulations.

3.7.3. Reporting procedures

For each SAE, the Investigator will complete a SAE Report Form in English and assess the relationship of each SAE to study treatment. The completed form(s) should be sent by e-mail to the Sponsor within 24 hours of first knowledge of the SAE (as outlined in [Section 3.7.1](#) and [Section 3.7.2](#)). The initial SAE should be reported immediately, even if only preliminary information is available. Follow-up information should be sent by the same Investigator, restating the date of the original report. Either a new SAE form is sent (stating that it is a follow-up), or the original one is resent (with the new information highlighted and a new date provided). The follow-up should describe whether the event has resolved or continues, if and how it was treated, whether the blind was broken or not, and whether the patient continued or discontinued study participation. The form confirmation will be retained.

Pregnancy follow-up (as outlined in [Section 3.6.5](#)) should be reported to the IRB within 24 hours of first knowledge on a Pregnancy Report Form. Follow up will describe the outcome of the pregnancy, including any voluntary or spontaneous termination, details of the birth, and the presence or absence of any congenital abnormalities or birth defects.

